**Waivers to the inclusion/exclusion criteria will not be granted**

### **8.3. Enrollment**

Screening will continue until 48 subjects are qualified and randomized for the study. Subjects will not be considered enrolled in the study until the time of randomization

### **8.4. Allocation to Treatment**

Subjects will be assigned a unique Screening number upon entry in the eCRF, which will consist of a unique 2-digit site code (starting with 01) and a 2-digit subject number (starting with 01 at each site) indicating the sequence at which the subject was screened for eligibility. Subjects will keep this number throughout the study.

The randomization scheme is 1:1:1 for high dose, low dose and placebo. Each group will have 16 subjects, but the placebo group will be matched to high and low infusion rates (8 in each group). The randomization is stratified by site.

When the subject is qualified and the hypoglycemia induction procedure begins day 1, the subject will be randomized by the study coordinator by either a central randomization or by logging into the IWRS and requesting a treatment allocation. The site personnel will receive the blinded treatment allocation number for the study drug product.

### **8.5. Blinding**

For this study, subjects, investigators and study staff will be blinded.

The investigator has access to break the blind if necessary in emergency situations for reasons of subject safety. Whenever possible, the investigator or sub-investigator should consult the Sponsor prior to breaking the blind. When the blinding is broken, the reason must be fully documented and entered in the CRF.

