### **6.1.2.3. Glucagon Infusion Rate Selection**

A previous study (Edelman, ADA annual scientific sessions, 2006) evaluating continuous glucagon administration for the prevention of hypoglycemia tested doses at 2, 4 and 8 ng/(kg\*min) and found apparently no effect at 2 ng/(kg\*min), weak indications of effect at 4 ng/(kg\*min) and, given a modest sample size, reasonably clear effect at 8 ng/(kg\*min) with some but limited room for further effect.

These findings would suggest doses in the vicinity of 4 and 16 ng/(kg\*min) corresponding to 19.2 and 76.8 µg/hr for an 80-kg person would be well chosen in this proof-of-concept study. As further development would most likely lead to a device with a fixed infusion rate, the glucagon doses chosen for the study are 20 and 80 µg/hr, or given the formulation concentration of 5 mg/ml, infusion rates of 4 and 16 µl/hr. For the pump setting that measures in insulin U100 units that corresponds to 0.4 and 1.6 U/hr.

This highest dose to be tested in the study will allow a greater than 10x safety margin based on findings from a 28-day toxicology study in rats conducted with Xeris glucagon (see current Investigator's Brochure).

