## 7. STUDY DESIGN

### 7.1. Study Overview

This is a prospective, randomized, double-blind, parallel trial with the primary analysis after 4 weeks treatment with CSGI or placebo. As both the low and high dose group use the same formulation, the dose will be determined by infusion. To preserve the blind, the placebo therefore is administered by matching infusion methods to CSGI (high and low infusion rates, split to create the appearance of a 4-group trial on the schematic).

Study Schematic:

After a 1-week run-in on CGM, subjects will have key hormones of their hypoglycemia counter regulatory response quantified using a stepwise hypoglycemia induction. They will then receive investigational product for 4 weeks before discontinuation and reassessment of the same hypoglycemia counter regulatory response.

Treatment stops at 4 weeks, but subjects will continue blinded for 6 additional months to investigate duration of response with assessments at 3 and 6 months. The primary endpoint will be tested at 4 weeks post randomization, but the double blind will remain intact until the end of the study.

Baseline Qualification:

Subjects will continue their insulin regimen as usual throughout the study, adjusted by the investigator to achieve ADA recommended targets.

After enrollment, the subjects will require approximately one week of CGM data prior to their baseline hypoglycemia induction procedure. Subjects will enter a run-in phase of 1 week wearing a blinded CGM device.

Subjects will arrive in the Clinical Research Unit (CRU) the morning of the planned hypoglycemia induction procedure. The CGM data will be retrieved. The following CGM criteria must be met: a minimum of 6 days must be recorded using the CGM before the subject will be fitted with a new CGM device. If the CGM criteria are not met, the subject is inserted with another CGM for renewed baseline period. Should the second baseline period not yield eligible CGM data, the subject will stop further participation in the screening procedures.

The subject will fast after midnight. The subject's arms are cannulated venously, one side for both insulin and glucose infusion and the other side for venous sampling. The subject will stop their own insulin treatment and receive IV insulin and IV glucose to maintain their plasma glucose between 80 to 120 mg/dL, as measured by either BGM or YSI. They will remain fasting until the end of the hypoglycemia procedure the following day.

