## **9. STUDY PROCEDURES**

### **9.1. Outpatient Insulin Dose Adjustment During Run-in and Treatment Phases Weeks -1-4**

Subjects' insulin doses should be reviewed and adjusted to maintain current ADA recommended glycemic targets of pre-prandial PG of 80-130 mg/dL and post-prandial PG<180 mg/dL, per investigator's discretion.

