**9.4.4. Hypoglycemia Induction and Stabilization, 2nd Step**

1. The GIR will be decreased with the goal of achieving a PG change rate of  $-1 \text{ mg/(dl*min)}$  to achieve the target of  $50 \text{ mg/dL}$  but no greater than  $54 \text{ mg/dL}$ .
2. The PG will be measured every 5 minutes for thirty minutes:
  - a. If 1 PG measurement is greater than  $54 \text{ mg/dL}$  during the thirty minutes; the 2nd step will re-start, per investigator discretion.
3. At every PG measurement the estimated time to the  $50 \text{ mg/dL}$  target will be assessed and the GIR adjusted accordingly.
  - a. Plasma Glucose and assessment of hypoglycemia symptoms will be measured and assessed every 5 minutes.
4. When the plasma glucose at  $50 \text{ mg/dL}$  has been maintained for a minimum of 30 continuous minutes, two sets of blood samples for assessment of counter regulatory hormones will be drawn 10 minutes apart (e.g. 30 and 40 minutes).

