12. Plasma glucose is measured using a laboratory quality instrument, e.g. the YSI 2300 or 2900 that will be used for the clamping procedure.
13. Insulin infusion should begin after the baseline venous blood samples are obtained. An IV glucose infusion should be started concomitantly.
14. Assessment of vital signs, including measurement of BP, after a 5-minute seated rest
15. The 100 mg/dL baseline prior to hypoglycemia induction will be assessed for adequacy or initiated as described in section 9.4.1.
  - a. When the baseline has been deemed adequate for at least 60 minutes two sets of blood samples for assessment of counter regulatory hormones will be drawn 10 minutes apart and processed.
16. The hypoglycemia induction including PG determination and hypoglycemia symptoms assessments (Appendix 2) will be executed as described in sections 9.4.2 to 9.4.5.
17. When hypoglycemia at 50 mg/dL has been held for 30 minutes, two sets of blood samples for assessment of counter regulatory hormones will be drawn 10 minutes apart and processed.
18. Treatment allocation and dispensing: The subject will be randomized as described in section 8.4, investigational product and Omnipods for the subject will be retrieved from storage.
19. When PG is >70 mg/dL in the normalization phase (section 9.4.6) the subject will be instructed in the filling and deployment of the OmniPod.
20. The study personnel will ensure the Omnipod flow rate is correctly set per protocol.
21. The subject will fill and deploy the first Omnipod under the observation of study personnel, insert and initiate the device as part of the training so that the subject can do this at home 2-3 days later.
22. The subject will be supplied with sufficient investigational product, Omnipods, and other study materials until the next weekly visit. The subject's training will include instructions to prepare a new Omnipod with the study drug for insertion, every 2-3 days.
23. Each time a new OmniPod is started local tolerability will be assessed as follows:

- a. Subjects will complete a Visual Analog (VAS) questionnaire regarding infusion site discomfort ([Appendix 3](#)) at **10±5** minutes, at **30±5** minutes and again at **180±5** minutes following the injection of study drug.

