### 7.10.5 Multiplicity

The analysis of the primary endpoint will be performed using a hierarchical hypothesis test in which an alpha of 5% will be preserved for each test. Testing will be employed in the following order:

- CSGI combined versus Placebo (if statistically significant <0.05, then the next hypothesis test will be conducted)
- CSGI high dose versus Placebo (if statistically significant <0.05, then the next hypothesis test will be conducted)
- CSGI low dose versus Placebo (if statistically significant <0.05, then the next hypothesis test will be conducted)
- CSGI high dose versus CSGI low dose

All secondary endpoints and the supportive analyses will be considered as descriptive evidence of efficacy and will be analyzed without any procedures to account for multiple comparisons.

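### The blind covers active versus placebo within a pump rate, not the rate itself; the SAP pools the two rate-matched placebo halves, leaving both single-dose tests partly confounded with rate and high versus low fully so

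*Protocol*

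**What the plan says.** Protocol 8.5 is unqualified: "For this study, subjects, investigators and study staff will be blinded".

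Protocol 7.1 explains that the two dose groups share a formulation and are separated only by how it is infused. Protocol 6.1.2.3 gives the settings: "For the pump setting that measures in insulin U100 units that corresponds to 0.4 and 1.6 U/hr". At Visit 3 (Protocol 9.5.3) a site task reads: "The study personnel will ensure the Omnipod flow rate is correctly set per protocol". Neither document describes an unblinded pump programmer or any concealment of the rate.

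The protocol handles this through the placebo. Section 7.1: "To preserve the blind, the placebo therefore is administered by matching infusion methods to CSGI". Section 8.4: "the placebo group will be matched to high and low infusion rates (8 in each group".

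The SAP does not use that matching. Section 7.3.2 has a single placebo column. Section 7.10.2 specifies a two-group t-test for each comparison, with no rate term. Section 7.10.5 tests, in fixed order, combined CSGI against placebo, high against placebo, low against placebo, and last "CSGI high dose versus CSGI low dose".

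**The concern.** A member of staff who sees 1.6 U/hr knows the subject is not on low dose; one who sees 0.4 U/hr knows the subject is not on high dose. Matched placebo keeps active or placebo status hidden within each rate, but it cannot hide the rate. Yet half of the pooled placebo group in each single-dose test ran at the other rate, and high against low compares two arms that rate-aware staff can tell apart.

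The outcome is an assayed hormone, so any influence has to be indirect. Two routes can be read from the protocol. Insulin is reviewed weekly (6.1.2.4) and adjusted "per investigator's discretion" (9.1), and section 6.1.2.2 holds that avoiding hypoglycemia partly restores the autonomic response. In the clamp (9.4.4), after one reading above 54 mg/dL the second "step will re-start, per investigator discretion".

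If either were handled differently by rate, the difference would be reported as a double-blind dose effect.

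**Working it through.** **Inputs.** Difference 1.5 nmol/L, SD 1.34 nmol/L, 80% power, alpha 5% (Protocol 11.1.3, SAP 5). Two-sided alternative (SAP 7.10.1). Minimum N of 42, raised to 48 (Protocol synopsis). 16 per arm, placebo 8 + 8 (Protocol 8.4). The rate shift δ is an assumption, taken as 0.25, 0.5 and 1.0 nmol/L and added to every high-rate subject, active or placebo; the documents give no value. All figures are for absolute change. The SAP's primary endpoint is percent change (SAP 4.1), for which no effect size or SD is stated.

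**The plan's own figure.** Two-sample t-test, power from the noncentral t with noncentrality 1.5 / (1.34·√(1/n₁ + 1/n₂)). Solving for 80% gives 13.56, so 14 per group and 14 × 3 = 42, as stated. Power is 81.3% for 14 v 14 and 86.5% for 16 v 16.

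**What rate alone reveals.** At either rate, 16 of 24 subjects are active, or 2/3. Overall it is 32 of 48, also 2/3. Rate carries no information on active against placebo.

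**Balance on rate and resulting bias** (bias = δ × difference in share on the high rate):

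| Test | Share on high rate | Bias |
|---|---|---|
| Combined v placebo | 16/32 v 8/16 | 0 |
| High v placebo | 100% v 50% | +δ/2 |
| Low v placebo | 0% v 50% | −δ/2 |
| High v low | 100% v 0% | +δ |

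**Simulation through the hierarchy** (each test run only if all earlier ones are significant), for δ = 0.25 / 0.5 / 1.0:

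- *No drug effect.* High v placebo is falsely significant in 2.5 / 2.4 / 1.8% of trials, low v placebo in 0.8 / 0.6 / 0.2%, and high v low in about 0.01%. Combined v placebo stays below 5%, falling to 3.7% at δ = 1.0 because the rate variance sits in the error term.
- *Both doses truly +1.5 nmol/L.* High v low is falsely significant in about 4 / 8 / 20% of trials. Stand-alone power for low v placebo falls from 86.5% to about 80 / 72 / 50%.

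**Rate as a factor in combined v placebo.** Unstratified SE = 1.34·√(1/32 + 1/16) = 0.410. Stratified SE = ½·1.34·√[2(1/16 + 1/8)] = 0.410. With no rate effect nothing is lost (about 94.7% power either way). At δ = 1.0 and a true 1.5 effect, power is 94.6% with the factor and 92.9% without.

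**Precision of the rate-matched estimates.** One dose against its 8 matched placebo subjects: SE = 1.34·√(1/16 + 1/8) = 0.58, power 69.5% for 1.5 nmol/L. Rate-corrected high minus low, that is (high − high-rate placebo) − (low − low-rate placebo): SE = 1.34·√[2(1/16 + 1/8)] = 0.82, 95% half-width 2.015 × 0.82 ≈ 1.65, power 43% for 1.5.

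**The case against.** The strongest reply is that the plan is largely protected already. Combined v placebo is first and balanced on rate, and the biases in the two single-dose tests run in opposite directions, so under a null drug effect the later gates almost never open. That stands. A reader who ran each test alone under the null would find high v low significant in 7.6 / 17.8 / 53% of trials and might take that as the trial's error rate. It is not, because the plan never runs that test alone.

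A reader might also infer that the dose-specific tests fall below 80% power. They do not: 69.5% belongs to a 16 v 8 contrast that nobody planned, and the planned 16 v 16 keeps 86.5%. Nor are high v placebo and low v placebo open comparisons. Vehicle is indistinguishable from drug (Protocol 8.6.1.2), both rates carry placebo, and rate only rules out the other active dose. It would also go too far to say subjects are unblinded to rate. They fill and change pods at home, but no passage says they see the setting; the documents establish rate knowledge for staff only.

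The mechanism is inferred too. The documents do not say that the staff who check the pump also titrate insulin or run the clamp. Titration follows glucose data and published targets, the restart is triggered by a measured value, and the hormones go to a central laboratory (Protocol 10.2). This makes a large rate shift less likely but does not rule one out. Finally, section 7.1 already discloses the split placebo. It does, but 8.5 does not carry the limit over and the SAP makes no use of the split.

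**Conclusion.** The point holds in a limited form. The blinding statement is broader than the design supports: masking is of active against placebo within a rate. The lead test, combined v placebo, is protected. High v placebo and low v placebo are partly confounded with rate, with active or placebo status still masked. High v low has no masking of rate.

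The consequence depends on an assumed shift. With no drug effect, no error rate in the hierarchy exceeds 5%. If both doses work equally at 1.5 nmol/L, the false high-v-low rate is about 4% at a shift of 0.25, 8% at 0.5 and 20% at 1.0, with a matching loss of power for low v placebo. So the risk is mainly to the dose comparison, in a phase 2a trial where that comparison is ranked last. These sizes are for absolute change and cannot be carried over to the percent-change primary.

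It is still worth acting on: the matched placebo subjects who could help separate a dose effect from a rate effect are already in the design and go unused.

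**What to change.** 1. Protocol 8.5 and 7.1: state that masking is of active against placebo within an infusion rate, and that rate is not masked to staff who set or check the pump.
2. SAP 7.10.2: include infusion rate (16 active and 8 placebo at each rate) as a factor in combined CSGI v placebo.
3. SAP 7.10.3: keep high v placebo and low v placebo as written. Add, as a sensitivity estimate with 95% CI, each dose against its 8 rate-matched placebo subjects, for percent change and for absolute change. Describe it as low precision, and quote about 70% power for absolute change only.
4. SAP 7.10.5: note that high v low is not masked for rate. The rate-corrected contrast may be shown beside it descriptively, with its precision (SE about 0.82 nmol/L, 95% half-width about 1.65 on the absolute scale).

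Cost: wording, one model factor (one degree of freedom) and a few estimates from data already held. The added intervals will be wide, and the blinding will read less favourably. No extra subjects, visits or procedures are needed.

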### **8.6. Supplies**

#### **8.6.1. Investigational Product**

##### **8.6.1.1. Drug Product Formulation and Packaging**

CSI-Glucagon™ is a room temperature stable, non-aqueous, injectable liquid formulation of glucagon. The formulation consists of 5 mg/mL synthetic glucagon peptide dissolved in a primary DMSO solvent, with trehalose added as a stabilizing excipient. A volume of 1 mL of formulation is filled into West Pharmaceutical's 2 mL Crystal Zenith® pre-filled cyclic olefin polymer (plastic) vial with Flurotec® coated stopper. The drug product is stored at controlled room temperature (20-25°C) prior to use.

##### **8.6.1.2. Matching Placebo**

The placebo consists of the vehicle for CSI-Glucagon, so it contains DMSO and trehalose, but no glucagon. The placebo is indistinguishable from the investigational drug and will be stored under the same conditions.

### **8.6.2. Drug Delivery Devices**

All OmniPod® devices to be used in the study are FDA approved and will not be modified in any way from their original state as provided by the manufacturer.

All devices will be stored at the hospital pharmacies where the clinical investigation takes place or in the investigators' offices prior to use in the clinical trial.

### **8.6.3. Preparation, Dispensing and Administration**

CSI-Glucagon™ and placebo will be supplied as 1 mL of non-aqueous solution in plastic Crystal Zenith (CZ) 2 mL vials. CSI-Glucagon™ will be transferred to the OmniPod® using the syringe and the fill needle supplied by the pump manufacturer. DMSO-compatible B Braun Injekt F® Low Waste Syringe 1 mL will be supplied by Xeris as backup. Each vial of CSI-Glucagon™ will be used to fill a single OmniPod® pump. If CSI Glucagon™ is not transferred into the OmniPod® within one hour of being drawn up into the syringe, the syringe, needle and drug should be discarded, and a fresh vial, needle and syringe should be used to fill the pod.

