Hypoglycemia induction procedure:

In the morning, insulin induced hypoglycemia ( $PG < 50$  mg/dL as measured by YSI) is achieved through a hyperinsulinemic clamp procedure.

The plasma glucose should be verified to be between the 80-120 mg/dL. The IV insulin infusion rate is then increased to  $20 \text{ mU}/(\text{body surface area (BSA)} \cdot \text{min})$  as a set rate and the subject's plasma glucose is stabilized at  $100 \pm 10$  mg/dL for minimally 60 minutes, through adjustments in continuous IV glucose. After this 60-minute stable period, the plasma glucose will be reduced to 70 mg/dL by decreasing the continuous IV glucose infusion rate. When the plasma glucose has been stable at  $70 \pm 5$  mg/dL for 20 minutes, a hypoglycemia symptom questionnaire administered, which will be repeated after 10 minutes.

The hypoglycemia induction will then begin, decreasing the continuous IV glucose infusion rate to bring the plasma glucose down to  $< 50$  mg/dL. Plasma glucose is measured every 5 minutes and the continuous IV glucose infusion rate is adjusted to achieve the target glucose concentration of  $< 50$  mg/dL. Hypoglycemia assessment will be administered every five minutes from this point until the end of the induction and PG recovery phase. When the target plasma glucose of  $< 50$  mg/dL has been achieved, blood samples for the assessment of counter regulatory hormones are drawn. Plasma glucose concentration will be measured and maintained at  $50 \pm 5$  mg/dL for 30 minutes after which another set of blood samples for the assessment of counter regulatory hormones are drawn and the hypoglycemia questionnaire re-administered. The insulin infusion is then stopped, and plasma glucose is raised to  $> 70$  mg/dL through the continuous IV glucose. The continuous IV glucose infusion is stopped once the subject's  $PG > 70$  mg/dL and the subject will be given a standardized meal. The subject is monitored until deemed medically stable for discharge, per investigator discretion.

Visit Overview:

After the completion of the first study visit (the baseline hypoglycemia induction procedure), the investigator will train the subjects to load, prime, and use the modified OmniPod. In this training, the subject will learn to prepare and use an OmniPod at a suitable infusion site. This includes direct observation of the subject when they attach and initiate the device, by the investigational staff.

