#### **9.5.4. Visit 4 – Safety check (Day 7±2)**

This visit can occur at any time of day as is least cumbersome for subject and clinic scheduling. The following will occur.

1. AEs since the last visit will be recorded.
2. Concomitant medication review.
3. Subject data including CGM, insulin utilization, electronic diary data will be uploaded to the MedTronic iPRO2 platform.
4. The subject's Omnipod will be removed.
5. The investigator or sub-investigator will use the modified Draize scales ([Appendix 4](#)) to assess erythema and edema formation at the injection site at 10±5 minutes following removal of the Omnipod. Any injection site with a score > 0 for either erythema or edema at 10 minutes post-dosing will be re-evaluated for both at 60±5 minutes post-dosing. If any scores remain > 1 at the 60-minute evaluation, the subject may leave the clinic but will be instructed to contact study staff if the condition fails to resolve.
6. Investigational Product and Omnipod accountability will be performed
7. The subject will load and initiate a new Omnipod with investigational product.
8. The subject will be given investigational product and Omnipods to cover time to next visit and will be instructed to exchange the Omnipod every 2-3 days.
9. Each time a new OmniPod is started local tolerability will be assessed as follows:
  - Subjects will complete a Visual Analog (VAS) questionnaire regarding infusion site discomfort ([Appendix 3](#)) at 10±5 minutes, at 30±5 minutes and again at 180±5 minutes following the injection of study drug.
  - Subjects will complete an Injection Site Discomfort Description and Duration Questionnaire ([Appendix 4](#)) at 10±5 minutes post-dosing. If discomfort is ongoing at 10 minutes post-dosing, the questionnaire will be completed again before the subject leaves the clinic to document the final duration.
10. The next visit will be scheduled
11. The subject will be reminded to keep his or her iPROmylog diary, bring used and unused Omnipods and investigational product vials back at the next visit

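### At the high infusion rate a 1 mL vial lasts 62.5 h, so a pod worn to the 72 h end of the permitted change interval can leave a compliant high-dose subject up to about 9.5 h without glucagon

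*Protocol*

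**What the plan says.** Protocol 6.1.2.3 sets doses of 20 and 80 µg/hr from a 5 mg/ml solution, which it converts to 4 and 16 µl/hr. It adds: "For the pump setting that measures in insulin U100 units that corresponds to 0.4 and 1.6 U/hr".

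On supply, Protocol 8.6.1.1 says that "A volume of 1 mL of formulation is filled into" each plastic vial, and 8.6.3 says that "Each vial of CSI-Glucagon™ will be used to fill a single OmniPod® pump". The usual syringe is the pump manufacturer's, with no size given; for the spare, "Low Waste Syringe 1 mL will be supplied by Xeris as backup". Pods are primed: under 7.1, "the investigator will train the subjects to load, prime, and use the modified OmniPod". No priming volume is given.

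On pod changes, item 22 of 9.5.3 (Visit 3) has "instructions to prepare a new Omnipod with the study drug for insertion, every 2-3 days", and item 21 uses the same interval. Item 8 of 9.5.4 (Visit 4) says the subject "will be instructed to exchange the Omnipod every 2-3 days", and Visits 5 and 6 repeat this by reference. At each of these weekly visits a fresh pod is started: "The subject will load and initiate a new Omnipod with investigational product".

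The documents state no vial overfill, no second vial for a pod, no maximum wear in hours, and no action for a pod that runs empty.

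**The concern.** The change interval is the same for everyone, but the two rates use up a vial at very different speeds. At the high rate the vial runs out inside the permitted interval. A subject can therefore follow every written instruction and still receive no drug for the last hours of a pod.

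Only the high-dose arm can lose active drug this way. That arm is half of the combined group in the first hierarchical test, and it enters the high-versus-placebo and high-versus-low tests directly. If gaps occurred, the regimen labelled 80 µg/hr would have delivered somewhat less, and those differences could be slightly diluted.

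The on-treatment glucagon measure is more directly exposed. Protocol 9.5.7 item 8 draws it at Visit 7 before the pod comes off, and Protocol 11.2 treats such values as steady state. Protocol 6.4 describes glucagon's half-life as extremely short, so a sample from a pod that has been empty for hours would not represent steady state at 80 µg/hr.

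**Working it through.** **Inputs.** Doses, concentration and rates: Protocol 6.1.2.3. Vial fill: 8.6.1.1 and 8.6.3. Change interval, 48 to 72 h: 9.5.3 and 9.5.4. Usable volume per pod, V, is not given beyond the nominal 1,000 µl, so a range is assumed below.

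**The plan's own figures reproduce.** 5 mg/ml is 5 µg/µl. 80/5 = 16 µl/hr and 20/5 = 4 µl/hr. At 10 µl per U100 unit these are 1.6 and 0.4 U/hr, as printed.

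**Pod life = V / rate.**
- High rate: 1,000/16 = 62.5 h.
- Low rate: 1,000/4 = 250 h.

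**Volume needed for a 72 h wear.**
- High rate: 16 × 72 = 1,152 µl, which is 152 µl (15.2%) above nominal. The gap is 72 − 62.5 = 9.5 h.
- Low rate: 4 × 72 = 288 µl, so no gap.

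**Wears with no gap at the high rate.** 48 h uses 16 × 48 = 768 µl. 60 h uses 16 × 60 = 960 µl, leaving 40 µl. Three equal wears in a week are 168/3 = 56 h each, below 62.5 h.

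**Share of the high dose delivered over 28 days (672 h)**, with nominal 7-day visits and a new pod at each visit. The gap per 72 h wear is g = 72 − V/16. A 2+2+3 day pattern has four such wears (loss 4g) and a 3+3+1 pattern has eight (loss 8g).

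| V (µl, assumed) | Empty at (h) | g (h) | 2+2+3 delivered | 3+3+1 delivered |
|---|---|---|---|---|
| 900 | 56.3 | 15.75 | 90.6% | 81.3% |
| 950 | 59.4 | 12.625 | 92.5% | 85.0% |
| 1,000 | 62.5 | 9.5 | 94.3% | 88.7% |
| 1,050 | 65.6 | 6.375 | 96.2% | 92.4% |
| 1,100 | 68.8 | 3.25 | 98.1% | 96.1% |
| 1,152 | 72.0 | 0 | 100% | 100% |

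**Time-averaged high dose at V = 1,000.**
- 2+2+3: 80 × (1 − 38/672) = 75.5 µg/hr.
- 3+3+1: 80 × (1 − 76/672) = 71.0 µg/hr.

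**Visit 7.** If the last wear of a 2+2+3 week is the three-day one, the pod in place at the glucagon draw is 72 h old and, at nominal volume, has been empty for about 9.5 h.

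**The case against.** The instructions are compatible over most of their range: 62.5 h lies between 48 and 72 h, and only the last 9.5 h of that 24 h window is a problem. A real gap also needs no usable overfill and a subject who keeps an empty pod on. Subjects are trained on the pump, and the training material is not in these documents. The 1 mL syringe is weak evidence because it is only the spare. Read literally, 8.6.3 stops a vial being split between pods but does not forbid a second vial, although none is provided for. All of this stands, which is why the gap is permitted rather than shown.

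The dose effect is also modest by the protocol's own yardstick. Section 6.1.2.3 derives 76.8 µg/hr for an 80 kg person before rounding to 80. Against that, 75.5 is 98% and 71.0 is 92%, and both are more than 3.5 times the low dose.

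The glucagon measure carries little inferential weight. Protocol 11.2.1 makes it descriptive, and the SAP's output list shows it only as Listing 16.2.8.2.

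A reader might take the 88.7% in the 3+3+1 pattern as a breach of the 90% expectation that would remove subjects from the per-protocol set. The documents do not support this: SAP 7.1.2 and section 10 dropped the 90% rule. Nor is the SAP's exposure definition at fault. SAP 7.2.6 already says it counts calendar time and disregards breaks, so an edit there would be redundant.

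**Conclusion.** The point holds as a minor, cheap improvement. The written instructions allow a high-rate pod to be worn 62.5 to 72 h, and within that band a compliant high-dose subject can be without glucagon for up to about 9.5 h per pod. This assumes a nominal 1 mL from one vial, no usable overfill, and an empty pod left in place. Priming or residual loss lengthens the gap, and net overfill of 152 µl removes it. The low-dose arm has no gap; high-rate placebo subjects run dry at the same time but lose only vehicle.

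A reader might infer that the high-dose arm was under-dosed, or that the primary comparison is compromised. The documents do not show either. They do not say how long pods were actually worn, and nothing in them shows that short interruptions alter the week 4 epinephrine response. The ITT comparison remains valid for the regimen as used. What remains is a possible modest dilution of the high-dose effect and a possible off-drug Visit 7 glucagon sample.

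**What to change.** **If dosing is ongoing.** In Protocol 9.5.3 items 21 and 22 and 9.5.4 item 8, replace the two-to-three-day interval with: *every 2 days, and no later than 60 h after pod start; if a pod empties earlier, replace it at once.* Apply this to all subjects so that the instruction does not reveal the rate. The 60 h ceiling leaves 40 µl for losses at nominal volume; set it lower if the sponsor's known priming and residual loss exceeds that. In 9.5.7 item 8, record the start time of the pod in place at the glucagon draw.

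**If dosing is complete.** Use Listing 16.2.5.1 where it holds change times. Otherwise state in the clinical study report that the delivered high-rate dose is unverified. Pod counts should not be relied on: three pods cover 3 × 62.5 = 187.5 h, more than a 168 h week, so a 3+3+1 week would not be flagged.

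**Cost.** A few lines of protocol text and somewhat more frequent changes. In a nominal 168 h week, 72 h wear takes 3 pods, and the 60 h ceiling can also be met with 3 (for example 60+58+50 h). Strict 48 h changes take 4. That is 0 to 4 extra pods and vials per subject over 28 days, at most 4 × 48 = 192 for the trial. Visits further apart than 7 days need supply sized to match.
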